## **METHODS**

To test our hypothesis, we conducted a survey among older Medicare beneficiaries with cLBP. "X university IRB" approval was received to conduct this study. This study was registered under clinical trials.gov website (NCT03669354).

### **Population**

Potential survey participants were identified through analysis of Medicare claims data. The study population included non-institutionalized Medicare Fee for Service (FFS) beneficiaries, either male or female, aged 65-84 years, as of 01/01/2012, and residing in a US state or the District of Columbia, and continuously enrolled in Medicare Parts A (inpatient), B (outpatient) and D (pharmacy) from 2012 through 2016. We restricted the population to subjects with an episode of cLBP beginning in 2013. cLBP has previously been defined as lasting three months or longer, thus, an episode of cLBP was identified by two paid claims for outpatient office visits with a primary diagnosis of LBP greater than 90 days but less than 180 days apart. Claims were further restricted to the clinician specialties of General Practice, Family Practice, Internal Medicine, Osteopathic Manipulative Medicine, Physical Medicine and Rehabilitation, Chiropractic, Physical Therapist in Private Practice, or Pain Management. Low back pain was identified by ICD-9 or ICD-10 diagnosis codes. We excluded all subjects with any diagnosis of cancer or use of hospice care. We assembled an analytic data set of claims for 28,160 Medicare beneficiaries who met study inclusion criteria. Study subjects were grouped into four cohorts as defined below. The research methods were reviewed and approved by the principal investigators' institutional review board.

### **Cohort Definitions**

All included patients received long term management of cLBP with SMT or OAT. SMT was identified in clinical claims data by Current Procedural Terminology (CPT) code 98940, 98941, or 98942. OAT was identified as opioid analgesics or analgesics containing opioids, identified by drug code and obtained by prescription through an outpatient pharmacy. For OAT, we defined long-term management as 6 or more standard 30-day supply prescription fills in a 12-month period. For SMT, we defined long-term management as  $\geq 12$  office visits for spinal manipulation for LBP in any 12-month period, including at least one visit per month. We assembled two primary and two crossover cohorts as follows:

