#### **Primary Cohorts**

SMT= Initiation in 2013 of long-term management with SMT, and no OAT for 12 months after initiating SMT

OAT = Initiation in 2013 of long-term management with OAT, and no SMT for 12 months after initiating OAT

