## **Data Analysis**

We generated descriptive statistics including computation of means for continuous variables and percentages for categorical data. We examined between-group differences for our three measures. Specifically, we first compared outcomes for the SMT and OAT cohorts to test our primary hypotheses and subsequently compared outcomes for the SMTX and OATX cohorts as exploratory analyses.

In order to address our primary hypothesis, we collapsed the response options as follows: response options for satisfaction with care items, 8-10, we coded as 'Very satisfied' and response options <8, we coded as 'Less satisfied'. We conducted Pearson chi-square tests to examine differences between groups for the Beliefs about Treatment items as well as for the overall satisfaction with treatment items.

Additionally, for the Beliefs about Treatment items, we combined the response options using the following categories: Disagree (combined Strongly disagree with Disagree), Agree (combined Strongly agree with Agree), Undecided was left as is. Group mean differences for the SF-12 mental and physical health scores were examined using *t*-tests. We performed *t*-tests for group mean comparisons utilizing the entire 0-10 scale for overall satisfaction as well. Additionally, we conducted the Kruskal-Wallis non-parametric test to accommodate non-normality in the distribution of the data for the Beliefs about Treatment items. All analyses were conducted using IBM SPSS (Version 23).

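### The SMT cohort must be treated in every month of a year while the OAT cohort needs only six fills, so the primary cohorts are selected unequally on persistence and the satisfaction analysis does not examine this

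*Combined protocol and SAP*

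**What the plan says.** The Cohort Definitions section sets a separate long-term rule for each treatment.

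- Opioids (OAT): "we defined long-term management as 6 or more standard 30-day supply prescription fills in a 12-month period". No spacing or monthly requirement is given.
- Spinal manipulation (SMT): at least 12 "office visits for spinal manipulation for LBP in any 12-month period, including at least one visit per month".

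Each rule carries its own literature citation. The difference between them is not discussed.

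The Primary Cohorts section builds on these rules. SMT is "Initiation in 2013 of long-term management with SMT, and no OAT for 12 months after initiating SMT"; OAT is "Initiation in 2013 of long-term management with OAT, and no SMT for 12 months after initiating OAT".

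The Data Analysis section makes this pair the main contrast: "we first compared outcomes for the SMT and OAT cohorts to test our primary hypotheses". Satisfaction is dichotomised ("response options for satisfaction with care items, 8-10, we coded as 'Very satisfied") and tested without adjustment: "We conducted Pearson chi-square tests to examine differences between groups". A t-test on the full 0-10 scale is added. No summary of months treated, adjustment for persistence or alternative threshold is described.

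**The concern.** A person treated intensively for six months who then stops can enter the OAT cohort but cannot enter the SMT cohort. Whether someone keeps up a voluntary treatment plausibly depends in part on what they think of it, and what they think of it is the outcome. Entry rules that demand different amounts of persistence can therefore create a satisfaction difference between two treatments that patients like equally well. The belief items are compared between the same cohorts and are exposed in the same way.

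A chi-square or t-test cannot tell such a difference from a real one. At stake is whether a difference between SMT and OAT can be read as a difference between treatments, or partly reflects how the cohorts were assembled.

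**Working it through.** The plan gives no sample size, target effect or bias estimate, so there is no figure of its own to reproduce. The thresholds below come from Cohort Definitions. Everything about how persistence relates to satisfaction is assumed.

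**1. The thresholds.** OAT minimum: 6 × 30 = 180 days; 180/365 = 0.493, or 49% of a year. SMT minimum: 12 of 12 months. Twelve visits in 12 months already average one a month, so the monthly clause adds something only if it means a visit in every month. A visit is one contact and a fill is 30 days of supply, so 12 against 6 is not itself the comparison. The asymmetry lies in the monthly requirement.

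**2. How unequally the rules select.** Assume one common monthly probability of use p, independent months, and one fill as one month of use. Then P(meets OAT rule) = Σ C(12,k) p^k (1−p)^(12−k) for k = 6 to 12, and P(meets SMT rule) = p^12.

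| p | OAT rule | SMT rule |
|---|---|---|
| 0.7 | 0.961 | 0.014 |
| 0.8 | 0.996 | 0.069 |
| 0.9 | 1.000 | 0.282 |

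If p varies between people as Beta(1,1), Beta(2,2) or Beta(2,1), those meeting the OAT rule average 9.0, 8.3 and 9.4 treated months, against 12.0 for the SMT rule.

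**3. What that could do to satisfaction.** In 2,000,000 simulated patients, both treatments have the same persistence distribution and the same satisfaction (50% very satisfied). A correlation ρ links persistence to satisfaction. The true difference is zero. The range in each row is over the three Beta distributions.

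| ρ | SMT − OAT, very satisfied (percentage points) |
|---|---|
| −0.2 | −8 to −9 |
| 0 | about 0 |
| 0.1 | +4 to +5 |
| 0.2 | +8 to +10 |
| 0.3 | +11 to +14 |
| 0.5 | +18 to +22 |

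**4. A second model, in which a patient who stops does not restart.** True scores s are normal with mean 6.5 and SD 2.5, rounded and held within 0-10. The monthly continuation probability is c(s), with logit c(s) = logit(c0) + b(s − 6.5). The first month is certain, so reaching month 12 has probability c^11 and reaching month 6 has probability c^5. The gap is the mean score weighted by c^11 (SMT) minus the mean weighted by c^5 (OAT), for c0 from 0.80 to 0.95.

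- Common slope b of 0.25 to 0.75: +0.37 to +0.78 points. For example, with c0 = 0.90 and b = 0.25, 7.67 − 7.10 = +0.57.
- b = 0: zero.
- Common slope −0.25: −0.37 to −1.01 points.
- SMT slope 0.25, OAT slope 0.75: +0.03 at c0 = 0.80, −0.21 at 0.90 (7.67 − 7.88), −0.34 at 0.95.

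**5. What an equal rule does.** With a common slope, a 12-of-12 rule in both cohorts gives identical weights and a gap of zero. With SMT slope 0.25 and OAT slope 0.75 at c0 = 0.90, the gap becomes 7.67 − 8.38 = −0.71, wider than the −0.21 under the stated rules. Equal month rules therefore equalise selection on persistence, but not necessarily on satisfaction.

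**The case against.** The strongest reply is that each rule is a cited working definition of long-term use for a different kind of treatment, so a literal match between visits and fills is neither natural nor required. Six fills is a floor with no spacing rule, so they may be spread across the year, and OAT members need not have stopped halfway. The cohorts were accrued from 2013 care, the surveys were mailed on 01/10/2020, and the satisfaction item asks about prescription drug therapy (PDT) rather than opioids specifically. A model that treats opinion while on treatment as the survey answer is therefore remote from what was measured. All of this stands, and it limits what a simulation can show.

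The OAT cohort also excludes anyone who received SMT within 12 months of starting, which removes some dissatisfied opioid users. That is true, but the mirror exclusion applies to SMT, so it does not address the unequal persistence rules.

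A reader might infer that the rules tilt the satisfaction result toward SMT as a matter of construction. The documents do not support that. The rules fix the direction of selection on persistence only. Persistence may also mark unresolved pain or, for opioids, dependence. With a negative link the tilt reverses, and even with two positive slopes it reverses in most settings tried when the OAT slope is the steeper. Nor do the documents show that only the more satisfied SMT users are kept.

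What the reply leaves untouched is that the primary cohorts differ by design on a plausible correlate of the outcome, and the analysis neither describes nor tests the consequence.

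**Conclusion.** The concern holds as a matter of unequal selection. The SMT cohort must show treatment in 12 of 12 months, the OAT cohort at least 180 days of supply (49% of a year), and the unadjusted satisfaction comparison makes no allowance for this. That part rests on the text alone.

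A bias in favour of SMT is plausible if satisfaction rises with persistence to a similar degree under both treatments. The documents give no figure for that link, so neither sign nor size can be determined. The simulated range, about −9 to +22 percentage points for correlations from −0.2 to 0.5, is illustrative. It shows that a modest link could produce a material gap where none exists; it does not estimate the bias in this study. Because the check is cheap and bears on the primary comparison, it should be done.

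**What to change.** Keep the cohort definitions for the main analysis and add one sensitivity analysis.

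- Repeat the SMT versus OAT satisfaction comparison with OAT limited to respondents whose opioid supply covers at least part of each of the 12 months. Derive this from the Part D claims used to build the cohorts. Use months covered rather than a fill in every month, because a fill longer than 30 days would make a fully covered patient fail a fill-based rule.
- Report the distribution of months treated in each cohort.
- Present the restricted estimate with its confidence interval beside the main result, judge it on estimate and interval rather than significance, and qualify the conclusion if the estimate changes materially. It should not be a pass-or-fail condition for the main claim.
- The text describes surveys already mailed and analyses already conducted, so label the analysis post hoc if results have been seen.

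The cost is one claims query and one re-run. It requires survey responses to be linkable to individual claims, which the documents do not describe. The restricted analysis will have fewer OAT respondents and a wider interval. It does not remove bias if persistence relates to satisfaction differently for the two treatments, and the report should say so.

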#### **Primary Cohorts**

SMT= Initiation in 2013 of long-term management with SMT, and no OAT for 12 months after initiating SMT

OAT = Initiation in 2013 of long-term management with OAT, and no SMT for 12 months after initiating OAT

#### **Crossover Cohorts**

SMTX = Any occurrence of SMT for cLBP in 2013, followed by initiation in 2013 of long-term management with OAT

OATX = Any occurrence of OAT for cLBP in 2013, followed by initiation in 2013 of long-term management with SMT

The date of accrual (index date) for patients into each cohort was the date of the first office visit associated with an episode of cLBP. For subjects with more than one episode of cLBP, only the first episode was counted for purposes of cohort accrual.

## **Survey Procedures**

Following cohort assembly, potential survey participants were selected by random sampling of subjects in each of the four cohorts. The list of potential survey participants was securely transmitted to the Centers for Medicare and Medicaid Services (CMS), and initial contact was made by CMS in the form of a Beneficiary Notification Letter, signed by the CMS Privacy Officer. This letter notified the selected Medicare beneficiaries of the opportunity to participate in a healthcare survey, and allowed them the option to decline participation via enclosed reply forms. Upon conclusion of this process, CMS provided us with contact information for beneficiaries that had been determined to be eligible for voluntary participation in the survey. CMS provided contact information for 2,490 participants; beneficiaries who were deceased or without contact information were removed. A total of 1,986 surveys were hand-addressed and mailed to the Medicare beneficiaries on 01/10/2020. All available phone numbers were used to make reminder phone calls and two weeks after initial mailing, 1,070 reminder surveys were re-sent to cohorts with lower response rates. The data was entered into an MS Excel spreadsheet, with double data entry and data verification. Patient's signed consent was obtained prior to participate in the study.

## **Outcome Measures**

### ***Overall Satisfaction with SMT and PDT***

The survey measured satisfaction for both SMT and PDT on a scale from 0-10, 0 being very dissatisfied and 10 being very satisfied. The patients were also given an option to select 'not applicable' if they never experienced either PDT or SMT. Literature indicates that for quantifying satisfaction among patients, Numeric Rating Scales can be used.

### ***Beliefs about Treatments Received***

This study included an 8-item assessment of participant beliefs regarding their treatment of SMT and PDT. These survey items were taken from a validated scale (patient's treatment belief low back pain questionnaire) developed by Dima et al., with permissions from the author(s). A modified version of LBP treatment belief questionnaire scale (LBP TBQ Scale) was used for this study. An example of a belief question was: "I think spinal manipulation is pretty useless for people with back pain," or "I believe Prescription Drug therapy (PDT) is pretty useless for people with back pain." Responses ranged from Strongly Disagree, Disagree, Agree, Strongly Agree and Undecided in a 5-point Likert scale. For purposes of analysis, we combined the response options into the following three categories: "Disagree" (Strongly Disagree and Disagree), "Agree" (Strongly Agree and Agree), and "Undecided"(left as is).

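### Belief items pool people who had a treatment with any who never did, so an SMT-versus-OAT difference need not be one in beliefs about treatments received

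*Combined protocol and SAP*

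**What the plan says.** All references are to the combined protocol and SAP.

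- **Beliefs about Treatments Received.** The outcome is introduced as follows: "This study included an 8-item assessment of participant beliefs regarding their treatment of SMT and PDT". On the answer format: "Responses ranged from Strongly Disagree, Disagree, Agree, Strongly Agree and Undecided in a 5-point Likert scale". The answers are collapsed to Disagree, Agree and Undecided. One example item reads "I think spinal manipulation is pretty useless for people with back pain"; the other makes the same statement about prescription drug therapy (PDT).
- **Overall Satisfaction with SMT and PDT.** Here inexperience is recorded: "The patients were also given an option to select 'not applicable' if they never experienced either PDT or SMT".
- **Primary Cohorts.** One cohort is defined by the rule "SMT= Initiation in 2013 of long-term management with SMT, and no OAT for 12 months after initiating SMT". The other cohort has the mirror-image rule, again limited to a 12-month window: "OAT = Initiation in 2013 of long-term management with OAT, and no SMT for 12 months after initiating OAT".
- **Data Analysis.** The main contrast is stated as "we first compared outcomes for the SMT and OAT cohorts to test our primary hypotheses". For the belief items: "We conducted Pearson chi-square tests to examine differences between groups for the Beliefs about Treatment items". Undecided stays as a category of its own. Neither this section nor any other filters or stratifies belief answers by whether the respondent ever had the treatment.

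**The concern.** Each primary cohort is defined by a 12-month absence of the other treatment. People who never had SMT are therefore likely to be more common in the OAT cohort, and people who never had drug therapy, if there are many, more common in the SMT cohort. For any one belief item, inexperience is then probably unequal between the two groups being compared.

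A respondent without experience may well choose Undecided more often than one with experience. A three-category test responds to that as readily as to a shift between Agree and Disagree. A significant result has at least two explanations: users in the two cohorts judge the treatment differently, or one cohort simply holds more non-users. The outcome's heading points the reader to the first, and the planned analysis cannot tell the two apart. The satisfaction items show that some respondents were expected to lack one of the treatments, yet the belief analysis does not use that information.

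The issue belongs to the primary comparison. Members of the crossover cohorts (SMTX and OATX) have by definition had both SMT and OAT.

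**Working it through.** **The plan's own figure.** There is none to reproduce. The documents give no significance level, respondent count, sample-size calculation or never-user share. The nearest figure is 1,986 surveys mailed across four cohorts, or 1,986 / 4 = 496.5 each if split equally; the number returned is not given. What follows is an illustration on assumed inputs.

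**Assumptions (not from the documents).**
- Two-sided alpha 0.05; 150 replies in each of SMT and OAT.
- Experienced respondents answer identically in both cohorts: Disagree 25%, Agree 60%, Undecided 15%.
- Never-users keep the same Disagree:Agree ratio but answer Undecided with probability u, where u = 15%, 30%, 50% or 70%.
- 5% never-users in the treatment's own cohort; q = 20%, 40% or 60% in the other.

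**Method.** Each cohort's distribution is a mixture: p = (1 − share) × experienced + share × never-user. With equal n per cohort, the noncentrality of the 2 × 3 chi-square (2 df, critical value 5.99) is

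λ = (n/2) × Σ d² / p̄,

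where d is the difference between cohorts in a category and p̄ the mean of the two proportions.

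**One case in full (u = 50%, q = 40%).**
- Never-users: 14.7 / 35.3 / 50.0%.
- Own cohort: 24.5 / 58.8 / 16.75%. Other cohort: 20.9 / 50.1 / 29.0%.
- d = 0.0360, 0.0865, 0.1225; p̄ = 0.2269, 0.5444, 0.2288.
- Σ d²/p̄ = 0.0057 + 0.0137 + 0.0656 = 0.0850; λ = 75 × 0.0850 ≈ 6.38.
- Probability of a significant result: 0.61.

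**All cases, n = 150 per cohort.**

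| Never-users answering Undecided | q = 20% | q = 40% | q = 60% |
|---|---|---|---|
| 15% (same as users) | 0.05 | 0.05 | 0.05 |
| 30% | 0.07 | 0.17 | 0.34 |
| 50% | 0.16 | 0.61 | 0.93 |
| 70% | 0.32 | 0.93 | 1.00 |

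If only 10% of the other cohort are never-users, 50–70% Undecided gives 0.06–0.08. In the most extreme cell (70%, q = 60%) the Undecided share is 17.75% in one cohort and 48% in the other.

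**A concrete table.** Take 100 respondents per cohort with counts 50/35/15 and 40/28/32. Expected counts are 45, 31.5 and 23.5. Chi-square = 2 × (5²/45 + 3.5²/31.5 + 8.5²/23.5) = 1.11 + 0.78 + 6.15 = 8.04, p = 0.018. The Disagree:Agree ratio is 1.43 in both (50/35 and 40/28), so the cohorts differ only in how many are Undecided.

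**Cross-check and effect of restricting.** A second set of assumptions was used: experienced answers 50/35/15%, and 50, 100 or 200 replies per cohort, with 20,000 simulated studies per scenario. The pattern was the same. With no never-users in one cohort, 50% in the other and u = 50%, the test was significant in 44%, 74% and 97% of studies by the noncentral calculation, and the simulations agreed. With equal never-user shares (30% in each) it stayed at 5%. Restricted to the experienced, the simulated rate was 0.048–0.055 in every scenario run.

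**The case against.** Four arguments on the other side have weight.

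1. **The items can be answered without experience.** Both examples are general statements about people with back pain, and someone who never had the treatment can sincerely hold such a belief. Satisfaction does presuppose treatment, which explains why only those items have the not-applicable answer. This stands: leaving out that answer is not in itself a defect. What remains is the mismatch with a heading and description that refer to treatments received.

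2. **The chi-square is not miscalibrated.** A reader might infer from the table that the type I error exceeds 5%. The documents do not support that. The stated contrast is between cohorts, and cohorts with different Undecided shares do differ. The probabilities above are power for that difference; they mislead only if the result is read as a difference among people who had the treatment. Undecided is also kept as its own category, so the pattern would be visible if all three percentages are reported.

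3. **Never-use is not documented.** A reader might infer that the OAT cohort never had SMT and the SMT cohort never had drugs. The rule covers 12 months after initiation in 2013, and the surveys were mailed in January 2020, so treatment before or after that window is possible. The SMT cohort is selected for no opioid therapy, whereas the survey asks about prescription drug therapy, which the text does not limit to opioids. Few in that cohort may be PDT never-users. The full questionnaire is not in the documents either, so a skip instruction cannot be excluded, though none is described.

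4. **Restricting to the experienced introduces selection.** It compares a nearly complete cohort with self-reported users from the other. This is a good reason not to replace the planned test, but not a reason against a sensitivity analysis beside it.

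**Conclusion.** The point holds as one of interpretation. The planned SMT-versus-OAT test answers whether the cohorts' belief distributions differ. It does not show whether people who had a treatment believe different things about it, which is what the outcome's name suggests.

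The size cannot be determined from the documents. Under the stated assumptions the probability of a significant result with no difference among the experienced runs from 0.05 to nearly 1. It stays at 0.05 if never-users choose Undecided no more often than users, or if never-user shares are equal. It becomes large only when never-users are both unequally distributed and markedly more often Undecided. The gap is likelier for the SMT items, through never-users in the OAT cohort, than for the PDT items. The count of not-applicable answers on the satisfaction items would show how far it matters.

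**What to change.** - Keep the full-cohort comparison and describe it as beliefs about the treatment, whether or not received.
- Add to Data Analysis, specified before it is run, a sensitivity analysis of each SMT or PDT belief item. Limit it to respondents who did not mark that treatment not applicable on the matching satisfaction item.
- Show never-users' answers in a separate column, with their number in each cohort.
- In every version, report the Undecided share separately from Agree versus Disagree.
- Conclude that beliefs about treatments received differ only if the difference also appears among the experienced.

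The cost is a filter and an extra table column in the existing SPSS analysis; no new data are needed. The restricted comparison has fewer replies, so a non-significant result there may reflect low power and should be read with the estimated percentages. The experienced members of the other cohort are a selected group, and the report should say so.
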